2.0 Hypotheses

Specific Aim 1: To determine whether change in weight loss is superior for those with prediabetes randomized to behavioral treatment for obesity + EFT (BT-EFT) versus behavioral obesity treatment (BT). We hypothesize that weight loss for BT-EFT will be superior to BT after 6 months of treatment.

Specific Aim 2: To determine whether change in HbA1c is superior for those with prediabetes randomized to behavioral treatment for obesity + EFT (BT-EFT) versus behavioral treatment (BT). We hypothesize that reductions in HbA1c for BT-EFT will be superior to BT after 6 months of treatment.

Specific Aim 3: To determine whether change in DD is superior for those with prediabetes randomized to behavioral treatment for obesity + EFT (BT-EFT) versus behavioral treatment (BT). We hypothesize that reductions in DD for BT-EFT will be superior to BT after 6 months of treatment.

Secondary Aim 1: To determine whether change in medication and behavioral adherence for hypertension and/or hyperlipidemia medications is superior for those with prediabetes randomized to behavioral treatment for obesity + EFT (BT-EFT) versus behavioral treatment (BT). We hypothesize that medication and behavioral adherence for BT-EFT will be superior to BT after 6 months of treatment.

Secondary Aim 2: To determine whether improvements in working memory are superior for those with prediabetes randomized to behavioral treatment for obesity + EFT (BT-EFT) versus behavioral treatment (BT). We hypothesize that working memory improvements for BT-EFT will be superior to BT after 6 months of treatment.

Exploratory Aim 1: To examine the relationship between baseline DD and DD change with weight loss, improvements in HbA1c and medication adherence. We hypothesize that baseline DD and DD change will predict weight loss, improvements in HbA1c and medication adherence.

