At the in person session 1 screening appointment, all participants will be given the Eating Disorder Examination (EDE) Questionnaire which is a well-established

and valid measure for eating disorders (J.M Mond et. al. 2004). If it is determined that they may have an eating disorder other than binge-eating disorder, the participant will not be eligible to continue with the study, and their physician may be notified. Binge-eating disorder or binge-eating disorder symptomology will not be considered exclusionary as behavioral weight loss treatment is both safe and effective for individuals with binge-eating disorder and binge-eating disorder symptomology (Grilo et al., 2011; Munsch et al., 2007). All participants who complete the EDE will be provided with a list of resources.

At the in person screening visit (session 1) documented consent will be obtained from potential participants. During the screening procedure, participants will be asked to sign a medical release form allowing the primary care physician to provide us with the information regarding eligibility and also allow us to send any pertinent medical information to their primary care physician (i.e. diagnoses of obesity, prediabetes, hypertension, dyslipidemia, depression score assessed by the BDI). If we do not receive the form within about 5 business days we will call to follow up with the primary care physician. Participants will also be asked to sign a release form for relevant pharmaceutical records (e.g. refill history of medications used to treat pre-diabetes, diabetes, and/or hyperlipidemia and hypertension) from their current pharmacy. Release of pharmaceutical records may be attained through the end of study participation if not attained at screening and will cover the period from about 90 days prior to screening to about the end of study participation. At the screening visit, participants will have their HbA1c levels measured by finger stick to obtain a drop of blood. If subjects meet eligibility criterion based on HbA1c levels (approximately 5.4% - 6.7%) at the initial screening visit, they may be eligible to participate regardless of confirmatory PCP diagnosis. Additionally, participants will be assessed for hyperlipidemia by finger stick and blood testing as well as for hypertension using an automated blood pressure machine.

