If participants are determined to be eligible (e.g., have an HbA1c measurement in the prediabetes range, are not pregnant, do not report alcohol or substance misuse, are able to adhere to all study procedures, etc.) they will be followed up by phone call or email (or preferred method of contact) within one week and scheduled for a baseline appointment. They will also be given a detailed orientation of what will be expected of them during the study, including tasks they need to complete, recording food consumption and activity levels, and frequency of visits to our lab. At the baseline assessment session, eligible participants may also be provided with an Actigraph WGT3X-BT accelerometer to measure physical activity. They will be instructed how to properly wear the accelerometer and asked to record a diary of its wear-time. After wearing the accelerometer for about 7 days, participants may be asked to visit the lab to return it. At the baseline session participants will also be instructed on how to complete a food recall, complete measures of delay discounting, behavioral economic demand, demographics, working memory, medication adherence, and physiological measures (e.g. HbA1c, cholesterol, weight, etc).

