After the first several weeks of treatment (about 6 weeks), eligible participants will be randomized to one of two groups, BT-EFT or BT. Participants in both groups will first attend weekly group meetings followed by bi-weekly group meetings, and then monthly group meetings for up to 6 months. Group sessions may be audio or video recorded so that if a participant misses the meeting, they are able to receive the information and learn the materials on their own time. They will be provided general information on healthy diet, physical activity and medication adherence. During the in lab appointments participants will be taught a number of behavioral treatment techniques. The treatment includes: 1) The Traffic Light Diet, which utilizes RED, YELLOW, and GREEN labels for food to guide participants toward the goal of consuming low energy dense, low glycemic, high nutrient dense foods; 2) the Traffic Light Activity Program, which also utilizes RED, YELLOW and GREEN labels for different levels of caloric expenditure, and 3) a variety of behavioral techniques, including stimulus control, self-monitoring, goal setting, problem solving, resetting rewarding mechanisms by reducing need for immediate gratification, finding behavioral substitutes for highly reinforcing food, and EFT (for the intervention group).

During each treatment meeting, participants will be weighed and then have a group session that lasts up to 60 minutes either preceded or followed by a session with a case manager that may last up to 30 minutes. The group sessions review information about weight loss and maintenance and engage in group problem solving for participants who are struggling with behavior change. During the individual meeting with their case manager, participants are taught behavior change techniques and review and address diet and activity self-monitoring and any barriers to adherence with the weight-loss behaviors.

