assessment sessions, participants may be sent an A1CNow test kit (PTS Diagnostics, *Sunnyvale, CA*), a commonly used self-administered A1c test that is available over-the-counter and that provides a valid measure of A1c (Chang et al., 2010), and may also be observed conducting the at-home A1c test by a staff member. In addition, participants may be sent an Actigraph with instructions on its use in order to assess physical activity for remote assessments. At the 3 and 6 month assessment sessions, an adverse event questionnaire will also be administered. After completion of the final assessment session, study staff will request records of participants' prescription refills from their current pharmacies and will be debriefed about the study. Participants may also be asked if they would be willing to anonymously complete a study evaluation on which participants can check a box to indicate whether or not they would allow their anonymous responses to be shared with others as testimonials. Research staff will be able to answer any questions the participant may have about the group they were assigned to at that time. For those consenting to be recontacted for a longer-term follow up, there may be an additional assessment at the 12-month time point that will entail follow-up measures of A1c, delay discounting and weight and could be conducted via video conferencing in the same manner as assessments done during the coronavirus mandatory closures. In addition, participants electing to complete the 12-month assessment will also complete the coronavirus and AE questionnaires.

Week #	Screening	0 (base line)	Month 1				Month 2				Month 3		Month 4	Mont h 5	Month 6	Month 12***
			1	2	3	4	5	6	7	8	9-10	11-12	13-16	17-20	21-25	~52 weeks
Group Meeting Topic*		Orien tation	TLD	TLD	Meal Planni ng	Phys ical Acti vity	Portion Contro l	EFT/C ontrol	High Risk Situatio ns	Stimulu s Control	Review, Portion Control	Shoppin g Healthy **	Self- monitorin g weight	EFT/RT in high risk situation s	Maintaini ng Healthy Habits**	
Review with Case Manager			X	X	X	X	X	X	X	X	X	X	X	X	X	
Primary Assessment Session		X										X			X	X
DD Assessment with EFT Cues									X				X		X	X
Wearing Actigraph		X										X			X	
Use Cues On MAMRT									Starts around week 7							
Compensatio n		X										X			X	X

*Group meeting topics are subject to change and may be presented in a different order.

**Group meeting content may be shared via video in lieu of in-lab group session.

*TLD = Traffic Light Diet

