Positive and Negative Affect Schedule (PANAS): The PANAS comprises two mood scales, one that measures positive affect and the other which measures negative affect (Watson et. al., 1988).

Medication Adherence (pill counts): Participants will be asked to bring their prescription bottles to both baseline and follow-up visits. Remaining pills will be counted and medication adherence will be calculated as: $(\text{quantity dispensed} - \text{remaining}) / (\text{quantity prescribed per day} * \text{days since last refill}) * 100$, yielding a measure of percent adherence. In addition, we will utilize participant refill history from their pharmacies to estimate prescription adherence from baseline to final assessment.

Medication Adherence (self-report): Participants will complete a self-report medication adherence questionnaire validated for use with patients with type 2 diabetes, yielding a measure of percent adherence.

Height, Weight, BMI: Participants' height will be assessed using a digital stadiometer. Participants' weight will be assessed using a digital scale. Based on the height and weight data, Body Mass Index (BMI) will be calculated according to the following formula: $BMI = \frac{kg}{m^2}$. These are the current standards set forth by the Centers for Disease Control and Prevention (Kuczmarski et al., 2002).

Blood pressure: Blood pressure will be measured 3 times using an OMRON automated blood pressure device by trained personnel. The latter two readings will be averaged.

Hemoglobin A1c (HbA1c): HbA1c will be measured using the A1CNow+® or A1CNow® self-check systems (PTS Diagnostics, Sunnyvale, CA) or the Alere Afinion™ AS100 Analyzer System (Abbott, Abbott Park, IL).

Blood Glucose: Blood glucose may be measured using the FreeStyle Lite Glucose Monitor or the FreeStyle Libre Pro (Abbott, Abbott Park, IL).

Cholesterol: Blood for lipid profile (e.g., total cholesterol, HDL, LDL, triglycerides, HDL/LDL ratio, etc.) will be measured using the Alere Cholestech LDX® system (Alere Inc., Coral Springs, FL).

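### Refill-based adherence is measured over one window that opens about 6 weeks before randomisation and has no pre-treatment value, which dilutes the EFT contrast on that measure

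*Combined protocol and SAP*

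**What the plan says.** Secondary Aim 1 (section 2.0) is framed as a comparison of change: "To determine whether change in medication and behavioral adherence for hypertension and/or hyperlipidemia medications is superior" in BT-EFT than in BT after 6 months.

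Section 12.0 gives three sources for medication adherence:

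- **Pill counts.** "Participants will be asked to bring their prescription bottles to both baseline and follow-up visits". The formula divides pills used by the number expected since the last refill.
- **Self-report.** A questionnaire giving percent adherence.
- **Refill history**, introduced as an addition to the pill counts: "we will utilize participant refill history from their pharmacies to estimate prescription adherence from baseline to final assessment".

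Section 11.0 lists adherence among the baseline-session measures ("working memory, medication adherence, and physiological measures") and collects it again at 3 and 6 months.

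Three other statements bear on the refill measure:

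- Section 11.0, on allocation: "After the first several weeks of treatment (about 6 weeks), eligible participants will be randomized to one of two groups, BT-EFT or BT". The schedule table says of cue use on the study website: "Starts around week 7".
- Section 9.0, on the pharmacy release, which "will cover the period from about 90 days prior to screening to about the end of study participation".
- Section 11.0, on when records are sought: "After completion of the final assessment session, study staff will request records of participants' prescription refills from their current pharmacies".

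Section 14.0 does not list medication adherence among the outcomes for the factorial ANCOVA. It brings in covariates only where the groups differ significantly in subject characteristics.

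**The concern.** Refill adherence is a property of a period, so the choice of period defines the outcome. The period in section 12.0 has three weaknesses.

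1. It starts at baseline (week 0), while the arms separate at about week 6. Refill behaviour in those first weeks cannot reflect EFT, yet it is averaged into the outcome.
2. No refill value is defined for the time before treatment. The measure therefore gives neither a change score nor a baseline covariate, although the aim is worded as change and the release already authorises the look-back records.
3. It ends at the final assessment, and the request for records is placed after that session. For a randomised participant who does not attend, the text gives neither an end date nor an instruction to request records.

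What is at stake is precision, and possibly completeness, on the one adherence source that needs neither bottles nor recall. Only participants on hypertension or hyperlipidemia medication contribute, so the numbers are probably small and avoidable loss of information matters more.

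**Working it through.** **Inputs from the documents.** Baseline is week 0 and randomisation is at about week 6 (section 11.0). The Month 6 column of the schedule covers weeks 21-25. Week 26 is added below as a calendar reading of 6 months. The release reaches back about 90 days, or 90/7 ≈ 13 weeks, before screening (section 9.0).

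**The plan's own figure.** The only sample size given is for delay discounting (section 14.0): standardised difference 0.72, power 0.80, alpha 0.05, 32 per group. A two-sided two-sample t-test solves to 31.3 per group, so 32, with power 0.81 at 32. The figure reproduces. No effect size, standard deviation or sample size is given for adherence.

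**Share of the window before randomisation**, f = randomisation week / final-assessment week:

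| Final assessment | f | 1 − f | True 10-point difference appears as |
|---|---|---|---|
| Week 21 | 6/21 = 29% | 0.71 | 7.1 |
| Week 25 | 6/25 = 24% | 0.76 | 7.6 |
| Week 26 | 6/26 = 23% | 0.77 | 7.7 |

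The multiplier 1 − f assumes no EFT effect before randomisation and a constant effect after it. The 10 points are an illustration only.

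**What this does to power.** Averaging over a longer window also changes the standard deviation, so the loss depends on the correlation ρ between adherence before and after randomisation. With unit standard deviation in each period, the standardised effect for the whole window is

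d(1 − f) / √[f² + (1 − f)² + 2f(1 − f)ρ].

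Take f = 0.24 and, purely as an assumption, borrow d = 0.72 with 32 per arm:

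- ρ = 0: effect 0.69, power 0.77
- ρ = 0.5: 0.72 × 0.76 / √0.8176 = 0.605, power 0.66
- ρ = 1: effect 0.55, power 0.58

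An outcome window starting at randomisation, without a covariate, keeps d = 0.72 and power 0.81. Adjusting it for a baseline refill value at ρ = 0.5 gives 0.72 / √(1 − 0.25) = 0.83, power about 0.91. The cut in residual variance is ρ²: 25% at 0.5 and 49% at 0.7. The documents give no value for ρ.

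**Length of the proposed outcome window.** 21 − 6 = 15 weeks to 25 − 6 = 19 weeks.

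**The case against.** The strongest reply is that Secondary Aim 1 does not rest on refill records. Pill counts and self-report are taken at baseline, 3 and 6 months, so change can be calculated from them. Because the pill-count formula runs from the last refill, a 6-month count mostly reflects recent use and normally avoids the dilution. This stands. A reader might infer that the aim cannot be tested as planned, and the documents do not support that. The gap belongs to the refill measure alone. The other sources have limits too: pill counts need bottles brought to visits, and the remote-assessment text in section 11.0 describes no pill count.

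A reader might also suspect bias. There is none from this source: both arms share the same pre-randomisation weeks, and a single-window comparison of randomised groups is valid without a baseline value.

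It can be said that the stated window might mean values at both ends, and that the 90-day release hints at an intended look-back. That may be so, but refill adherence needs a period and no baseline period is defined. Because the release spans the whole time, either window can be derived from the same records. The defect is one of derivation, not of lost data, for anyone whose records are obtained.

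On missing records, a reader might conclude that non-attenders' records will never be sought, or that the planned 20% attrition means up to a fifth of participants lose refill data needlessly. Neither follows. Section 11.0 gives the timing for those who finish and is silent on the rest. Section 16.0 stops further collection for those who withdraw, and some attrition may fall before randomisation. The documents give no count of randomised, non-withdrawn non-attenders, and it may be small.

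Finally, a window of 15-19 weeks may hold only one or two long-interval fills. That is a real cost of the remedy.

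**Conclusion.** The concern holds for the supplementary refill measure. About 24% of its window precedes randomisation (23-29% depending on the week of the final assessment), so a constant post-randomisation effect is multiplied by about 0.76 (0.71 to 0.77). The consequence is lost power, not bias. The measure also lacks a pre-treatment value, so by itself it cannot supply the change in Secondary Aim 1.

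The share rests only on the plan's own approximate weeks. The multiplier also needs the constant-effect assumption. The power figures are illustrations with a borrowed effect size, and the gain from adjustment depends on the assumed correlation. No number can be put on refill data lost through missed final sessions. This is worth correcting because the records are already authorised and the change is cheap, but it does not threaten the trial's main conclusions.

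**What to change.** - **Section 12.0.** Define two refill windows: (a) the roughly 90 days before screening, optionally extended to randomisation, as the baseline value; and (b) randomisation to the planned 6-month date as the outcome. Extending (a) uses the weeks closest to the start of EFT and is still free of any effect of allocation.
- **Analysis.** Compare arms on (b) by ANCOVA adjusting for (a), with the covariate fixed in advance. Record this in section 14.0, which at present lists no adherence analysis and makes covariates depend on observed group differences.
- **Section 11.0.** State that records are requested at the planned 6-month date for every randomised participant with a signed release who has not withdrawn, whether or not the final session was attended.

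The cost is protocol and SAP wording plus a few extra pharmacy requests. There are no new visits and no added burden on participants, and the look-back records are already within the release. The price in measurement is the coarser window of about 15-19 weeks for long-interval fills. The whole-period estimate can be kept as a sensitivity analysis from the same records.

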13.0 Setting

This research will be conducted at the University at Buffalo (UB) and Virginia Tech University (VT). All facilities are locked and require key or badge access to enter in relevant research areas.

The UB team will conduct research at the Division of Behavioral Medicine Research Labs, University at Buffalo South Campus.

The VT research team will conduct research at the Addiction Recovery Research Center at the Virginia Tech Carilion Research Institute. Recruitment and screening will be in collaboration with Carilion Clinic Department of Family and Community Medicine in Roanoke and surrounding areas.

Virginia Tech Carilion Research Institute will follow the same scientific and ethical review structure as the University at Buffalo. All research staff working on the project will need to complete Human Subjects Training as per the University requirements. Staff will be trained across sites to follow the same procedures and weekly/monthly meetings will be organized to ensure this.

14.0 Statistical Analysis Plan

Analytic plan is to use factorial ANCOVA to compare between group differences in different measures of DD, executive function, weight loss, changes in metabolic control, dietary composition, and physical activity for subjects randomly assigned BT-EFT/BT. Covariates will be used if significant differences between groups are observed in subject characteristics. We predict a main effect of EFT such that EFT will reduce the discounting, improve metabolic control, and increase weight loss compared to BT subjects.

The estimated sample size for this study is based on an ESD for reducing DD of 0.72 in obese/overweight subjects. In our pilot study of EFT vs control in a weight control program we observed even larger ESD of 1.64 for weight and 1.04 for energy intake. Based on ESD = 0.72 for DD, using power of 0.80 and alpha of 0.05, we can detect differences between groups in DD with 32 subjects per group, 64 total. Since we are anticipating 20% attrition for the field study, we will recruit 78 persons with prediabetes to start.

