6.0 Local Number of Subjects

Up to 200 subjects will be enrolled at the University at Buffalo (up to 400 nationally). The second site is located at Virginia Tech Carillon Institute, local PI, [name]. We expect about 25% of participants to meet our in-lab screening criteria, 20% of those participants subjects to drop out and about 80 subjects will complete the study. In addition, a small sample (approximately 4-6

subjects) will be assigned to be pilot participants to help with quality assurance and data validity procedures. Participants will be informed if they are a pilot participant at the time of consent.

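### Covariates enter the ANCOVA only after a significant between-group difference, and neither the baseline outcome nor site is fixed in advance: the cost is precision and a pre-specified model, not type I error

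*Combined protocol and SAP*

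**What the plan says.** Section 14.0 (Statistical Analysis Plan) is the whole analysis plan. On the model it says: "Analytic plan is to use factorial ANCOVA to compare between group differences in different measures of DD", and it goes on to list executive function, weight, metabolic control, diet and activity. On adjustment it says only: "Covariates will be used if significant differences between groups are observed in subject characteristics". It does not list the characteristics, give a test or threshold, or say whether they include the baseline value of the outcome. The only factor identified is treatment arm, so the second factor implied by a factorial model is unnamed.

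The sample size rests on an unadjusted two-group comparison of delay discounting (DD) at an effect size (ESD) of 0.72, power 0.80 and alpha 0.05: "we can detect differences between groups in DD with 32 subjects per group, 64 total". For weight the same section reports a pilot in which "we observed even larger ESD of 1.64 for weight and 1.04 for energy intake". It gives no effect size for HbA1c.

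Other sections bear on what could be adjusted for:
- Section 13.0 names two sites. No section describes randomisation stratified by site.
- Section 11.0 collects weight, HbA1c and DD at baseline, 3 months and 6 months, so week 0 values exist.
- Section 11.0 also places randomisation after treatment has begun: "After the first several weeks of treatment (about 6 weeks), eligible participants will be randomized to one of two groups, BT-EFT or BT". The word baseline therefore needs a date.
- The section 11.0 schedule table starts DD assessment with EFT cues at about week 7, and section 12.0 estimates refill-based adherence over the whole period from baseline to final assessment. Neither has a week 0 value.

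**The concern.** The reason to adjust for a covariate in a randomised trial is that it predicts the outcome. A significance test of baseline differences does not address that. Among all those randomised, any difference in a pre-randomisation characteristic arose by chance, so the test picks covariates by the luck of the allocation. A strongly prognostic variable that happens to be balanced is left out, and a useless one that happens to be imbalanced is let in.

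Two things are at stake. First, the model for the primary outcomes depends on the data, because nobody can say before unblinding which terms it will contain. Second, if the rule governs the baseline value of the outcome, the trial usually gives up precision that is available from data it already collects.

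**Working it through.** **1. Reproduce the plan's figure.** Inputs from section 14.0: ESD 0.72, power 0.80, alpha 0.05. A two-sided two-sample t-test needs 31.27 per arm, rounded up to 32, which matches. (One-sided would give 25, so the plan is two-sided.) At 32 per arm the noncentrality is 0.72 × √(32/2) = 2.88 on 62 degrees of freedom, and exact power is 0.809. No covariate enters this calculation.

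**2. How often the rule fires.** At an assumed 5% threshold, a given pre-randomisation variable is selected in about 5% of trials (4.9–5.2% in simulation) and omitted in about 95%. With k independent characteristics tested, the chance that at least one enters is 1 − 0.95^k: 23% for k = 5 and 40% for k = 10.

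**3. What always adjusting for baseline gains.** Let ρ be the baseline-to-follow-up correlation, with equal variances at both times. The documents do not give ρ, so it is assumed and varied.
- Follow-up value analysed: adjustment multiplies the residual variance by 1 − ρ².
- Change score analysed: the factor is (1 − ρ²) / [2(1 − ρ)] = (1 + ρ)/2.

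The ESD on the adjusted scale is 0.72 / √factor. At ρ = 0.5 both factors are 0.75, giving 0.831. For change scores, ρ = 0.7 gives 0.72/√0.85 = 0.781 and ρ = 0.9 gives 0.72/√0.95 = 0.739. The gain for change scores therefore shrinks as ρ rises.

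**4. Simulation of the rule.** 32 per arm, normal outcomes, ESD 0.72 on the analysed scale, two-sided 0.05; the baseline enters only if its between-arm t-test has p < 0.05. There were 40,000 trials per power setting (standard error about 0.002) and 80,000 for type I error. The site term is simulated with no true effect.

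| Outcome analysed | ρ | Never adjusted | Rule | Always baseline | Baseline + site | Type I error, rule |
|---|---|---|---|---|---|---|
| Follow-up | 0.5 | 0.8093 | 0.8173 | 0.8999 | 0.8940 | 0.0435 |
| Follow-up | 0.7 | 0.8066 | 0.8250 | 0.9752 | 0.9734 | 0.0362 |
| Follow-up | 0.8 | 0.8086 | 0.8305 | 0.9965 | 0.9959 | 0.0317 |
| Change | 0.5 | 0.8099 | 0.8187 | 0.8997 | 0.8954 | 0.0430 |
| Change | 0.7 | 0.8077 | 0.8129 | 0.8600 | 0.8549 | 0.0456 |
| Change | 0.8 | 0.8112 | 0.8148 | 0.8441 | 0.8375 | 0.0475 |
| Change | 0.9 | 0.8085 | 0.8092 | 0.8209 | 0.8155 | 0.0489 |

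For the follow-up value at ρ = 0.3 (100,000 trials) the rule gives 0.812 against 0.838.

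**5. Reading the table.** The rule barely improves on never adjusting. The change-score rows fit the plan's wording better, because section 14.0 describes weight and metabolic control as loss or change. In those rows the gain from baseline alone falls from 0.081 at ρ = 0.5 to 0.012 at ρ = 0.9. With site also in the model, the gain at ρ = 0.9 is 0.8155 − 0.8092 = 0.006. A site term of no value costs less than 0.01 in every row.

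**6. The other primary outcomes.** At the pilot ESD of 1.64, power for weight exceeds 0.999 with or without adjustment, so the gain there is a narrower interval. HbA1c has no stated ESD, so no power figure can be given.

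**The case against.** The strongest reply is that ANCOVA, in ordinary use, already contains the baseline value, and that the sentence about covariates concerns additional characteristics. On that reading none of the power loss above applies to the baseline outcome. This stands as a possibility: the text neither says so nor rules it out. It does not rescue the selection of other covariates by significance test.

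Other points have weight:
- **Factorial may mean arm by time, not arm by site.** Outcomes are collected at three times. If baseline is one of the repeated responses, a single-time comparison is not the plan's model; with complete data, the arm-by-time contrast from baseline to 6 months is the change-score comparison. The word needs defining under either reading.
- **The largest gains (0.975 and 0.997) require the raw follow-up value to be analysed**, which is the less natural reading for weight and metabolic control.
- **No benefit from site can be shown.** The documents give no between-site variance or split. The case rests on group treatment delivered at two sites.
- **Chance describes imbalance among everyone randomised.** Section 14.0 expects 20% attrition, and section 16.0 allows non-adherent subjects to be removed from the analyses, so an imbalance in the analysed set need not be chance. That limits the 95% figure but does not make a significance test a sound selector.

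A reader might infer that the rule inflates type I error. Applied as written to one baseline covariate, it does not: the simulated error is 0.032 to 0.049. A reader might also infer that the plan definitely leaves baseline out, or that the trial is underpowered because of the rule. The documents support neither: the first is unstated, and power for DD under the rule at the planned 32 per arm stays at about 0.81 or above in the settings examined.

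**Conclusion.** The point holds as a correctable weakness. The plan selects covariates by a method that ignores prognostic value and leaves the model open until the data are seen; this holds on any reading of ANCOVA.

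The power cost is conditional. It requires that the rule governs the baseline outcome, that 0.72 is on the analysed scale, that the threshold is 5%, and that the assumed correlations are about right. On those terms the loss for DD is about 0.08 in power at a correlation of 0.5. For change scores it is about 0.05 at 0.7 and about 0.01 at 0.9. Confidence is high on the gap in the text and much lower on its size, which the documents do not determine. The trial's validity is not in question.

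**What to change.** Replace the covariate sentence in section 14.0 with:

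> The arm comparisons of weight, HbA1c and DD (assessed without cues), and of any other outcome measured at week 0, include arm, the week 0 value of that outcome and site as fixed terms, whatever the observed baseline differences. Outcomes with no week 0 value (DD assessed with EFT cues, refill-based adherence) include arm and site only. No covariate is selected by a significance test of baseline differences.

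Name the second factor in the factorial model (site or time), or delete the word. If it is time, use the baseline value as a covariate and the 3- and 6-month values as responses.

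The cost is SAP wording and two degrees of freedom out of 62 at 32 per arm; no new data are needed. If both added terms proved worthless, simulated power would fall from 0.8085 to 0.7960, about 0.013. A worthless site term alone costs under 0.01.
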